4.1. Subject Disposition

Summary statistics (arithmetic mean, standard deviation, median, minimum and maximum for quantitative variables) will be presented by MT-3724 treatment group. Frequency tables for qualitative data will be provided. If not otherwise mentioned the summary statistics will be based on all subjects who received at least one dose of any study medication, the safety analysis set.

Subject disposition will be tabulated and include the following:

- The number of subjects screened
- The number of subjects treated in total
- The number of subjects in each population for analysis, and the reasons for exclusion, as applicable
- The number of subjects who withdrew prior to completing the study and reason(s) for withdrawal
- The number of subjects who completed the core study, and the number continuing into the repeat cycles and/or extension study.

A by-subject data listing of study completion information including the reason for premature study withdrawal, if applicable, will be presented.

4.2. Demographics and Baseline Characteristics

4.2.1. Demographic characteristics

The following baseline demographic characteristics will be summarized:

- age at enrollment
- gender
- race
- height
- weight

4.2.2. Medical history

Medical history findings include previous diagnoses, diseases and surgeries, excluding study indication, and meeting the following criteria: start before signing of the informed consent and considered relevant for the subject's study eligibility.

These data will be summarized using frequency tables for subject count by MedDRA v17.0 system organ class (SOC) and preferred term (PT). Summary statistics will be provided by MT-3724 treatment group and overall. Medical history will be provided in a by-subject data listing by treatment group.

4.2.3. Disease history

The following disease history parameters will be summarized:

- Age at diagnosis
 - In Part 1, the age at initial diagnosis will be assumed to be based on the first entry on the disease diagnosis field of the eCRF. In Part 2, the initial diagnosis will be indicated on the updated eCRF. The age at diagnosis will be computed as date of initial diagnosis – date of birth + 1. For patients enrolled under Protocol Version 7.0, the date of birth is not available; therefore, the year of birth will be used to approximate the age at diagnosis.
- Duration of disease
 - In Part 1, the duration of disease will be assumed to be based on the first entry on the disease diagnosis field of the eCRF. In Part 2, the initial diagnosis will be indicated on the updated eCRF.
- Tumor burden
- Tumor stage at diagnosis
- NHL histological diagnosis. If any data is missing from the initial disease diagnosis assessment, data will be taken from the disease diagnostic review assessment.

Disease history will be provided in by-subject data listings by treatment group.

4.2.4. Prior Medications

The prior medication will be analyzed using frequency tables based on the data classified by the WHO-DD ATC classification, version March 2014. The tables will include the corresponding name of the WHO DD code and the generic drug name. A medication is considered prior if the start date of the medication is before the date of first dose of MT-3724.

By-subject listings will be provided for all prior medications data by treatment group.

4.2.4.1. Prior Systemic Anti-Cancer Therapy

Descriptive summary statistics are not possible given the structure of the eCRF form that captured this data. Therefore, the individual prior systemic anti-cancer therapies (which include chemotherapy, hormonal therapy, immunotherapy and non-conventional therapy) will be presented in a by-subject listing for each treatment group.

Subjects who received anti-CD20 monoclonal antibody therapies will have their best response tabulated.

4.2.4.2. Prior Anti-Cancer Radiotherapy

Prior anti-cancer radiotherapy includes radiation therapy. Subjects who received radiation therapy will be tabulated. Individual prior anti-cancer radiotherapy will be presented in a by-subject listing for each treatment group.

4.2.4.3. Prior Anti-Cancer Surgeries

Prior anti-cancer surgeries include any prior diagnostic or therapeutic procedures. Subjects who underwent procedures will be tabulated. Individual prior anti-cancer surgeries will be presented in a by-subject listing for each treatment group.

4.2.5. Serum Rituximab levels

Subjects will be tabulated as positive or negative based on the clinical cut off value of 500 ng/mL. By-subject listings of serum Rituximab levels will be provided by treatment group.

4.2.6. Other baseline characteristics

[figure not shown]
Each subjects' functional status as measured by ECOG will be tabulated and listed in a by-subject data listing by treatment group.

Tumor imaging(MRI, CT, and chest radiography) and pregnancy test results will be provided in by-subject data listings by treatment group.

4.3. Exploratory Efficacy Evaluation

2.

Descriptive statistics for all of the above endpoints will be summarized by treatment group. By-subject listings will be provided for each treatment group.

No formal hypothesis-tests are planned.

4.4. Pharmacokinetic Evaluation

Pharmacokinetic analyses will be conducted using the PAS.

Analysis of PK and PDn parameters will be described in a separate PK/PDn analysis document.

A by-subject listing with all sampling times will be presented.

4.5. Study Drug Exposure

Study drug exposure analyses will be conducted using the Safety Set.

All study drug exposure analysis will also be performed by subgroup as defined in Section 3.8.

Study drug exposure will be calculated as the number of days subjects were administered study drug, as determined below, and will be summarized by treatment group using descriptive statistics.

$$\begin{aligned} \text{Duration of Study Drug Exposure (days)} \\ = (\text{Date of last infusion} - \text{Date of first infusion}) + 1 \end{aligned}$$

The number of dosing cycles completed will be tabulated for each treatment group.

Total drug received (both in mcg and mcg/kg), dose intensity (defined as total drug received divided by duration of exposure), number of doses taken, number of missed doses, number of dose interruptions, duration of dose interruption, and number of dose reductions will also be summarized.

Dosing information for each subject will be presented in a data listing by treatment group.

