1.3. Study Design

1.3.1. Synopsis of Study Design

1.3.1.1. Main Study

This is an open-label, phase 1/1b, dose-escalation study of MT-3724. There are two parts to this study, which include Part 1: Evaluating doses of MT-3724 in subjects with relapsed, refractory B-cell NHL or CLL to determine the MTD; and Part 2 (implemented in version 6.0 of the study protocol): The MTD cohort was expanded to evaluate safety, tolerability, and potential efficacy at the MTD. Implemented in version 7.0 of the study protocol, up to 40 additional subjects with DLBCL will be treated with MT-3724 at the adjusted MTD (50 mcg/kg/dose).

Part 1: The first 12-day course of treatment will be followed by at least 16 days of observation to provide a 28-day safety assessment following initiation of dosing. Each additional treatment cycle will be at least 21 days in length. In Part I, the first treatment cycle is 28 days (Core Study). All subsequent cycles (Cycles 2 – 5, Repeat Dosing Study) will be 21-day cycles. Subjects may receive up to 5 total cycles in the absence of clear disease progression or toxicity. If a subject achieves complete remission (CR), post Cycle 2, then 2 additional cycles will be attempted, after which dosing may be suspended.

Part 2: Each treatment cycle will be at least 21 days in length. Subjects may receive up to 5 total cycles in the absence of clear disease progression or toxicity

Parts 1 and 2: Retreatment under a separate extension protocol will be considered for subjects who exhibit PR or SD after completing 5 cycles (or 2 cycles after a complete remission) in consultation with the Sponsor.

Schematics of Parts 1 & 2 of the main study is presented in Figures 1 and 2.

Figure 1: Part 1 Study Schematic

[figure not shown]
[figure not shown]

Figure 2: Part 2 (MTD Expansion) Study Schematic

Core Study (Cycle 1, Days 1 to 28)

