All subjects will receive a single course of study drug via a 2 (\pm 15 minutes) IV infusion of MT-3724 on Days 1, 3, 5, 8, 10 and 12. Each dose of MT-3724 will be at the adjusted MTD (50 mcg/kg/dose). Three subjects were started in Part 2 at 75 mcg/kg/day but later had possibly related TEAEs that required dose reduction or a treatment discontinuation. Following the first dose in each cycle, there will be a minimum 21-day observation period for each subject prior to initiating the next treatment cycle. Subjects experiencing a serious adverse event (SAE) attributable to MT-3724 may be withdrawn from the study or depending upon the nature of the

event, the Investigator, in consultation with the DMC, may, once the event has resolved, resume dosing at a dose reduced by 25-33%. Subjects will have successfully completed a cycle if they receive at least 4 of the 6 infusions in that cycle, and they are followed for 21 days after their first dose in that cycle. If a subject completes less than 4 of the 6 infusions in the first 12 days of a cycle and the missed infusions were not due to an event that would contraindicate further dosing, then the Investigator in consultation with the Sponsor may attempt to achieve a minimum of 4 infusions by administering the missed doses in the third week (Days 15 - 19) of that cycle. In such instances, subjects must still be observed for a minimum of 21 days following the first dose in Cycle 1 prior to initiating any further study drug dosing. No dose escalation will be permitted above the adjusted MTD (50 mcg/kg/dose) identified by the DMC. However, at the Investigator's discretion, the dose for any subject in the Part 2 expansion cohort may be reduced by 25-33% for one or more doses in any cycle (see below) based upon a subject's response at the adjusted MTD (50 mcg/kg/dose).

Subjects must receive a minimum of 4 of the 6 infusions in a cycle in order to successfully complete that cycle and continue in the study. For subjects in Parts 1 and 2 who complete **at least 4** of the 6 infusions in any cycle, and the missed infusions were not due to an MT-3724-related event that contraindicates further dosing (see above for criteria for continued dosing), then up to 5 total cycles may be administered on the same schedule (Days 1, 3, 5, 8, 10 and 12) and at the same dose (as long as that dose is not subsequently identified to be a toxic dose).

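### The SAP's dose-intensity denominator leaves out the rest period after the last infusion, so the measure is biased upward, generally most for early stoppers, and can mask under-dosing

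*SAP*

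**What the plan says.** SAP 4.5 (Study Drug Exposure) states: "Study drug exposure will be calculated as the number of days subjects were administered study drug, as determined below". The formula beneath it is the date of the last infusion minus the date of the first infusion, plus 1. The same section then lists "dose intensity (defined as total drug received divided by duration of exposure") among the quantities to be summarised, with that duration as the denominator.

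The schedule is in SAP 1.3.1.1. For Part 2: "Each dose of MT-3724 will be at the adjusted MTD (50 mcg/kg/dose"), given by "IV infusion of MT-3724 on Days 1, 3, 5, 8, 10 and 12". On length: "Part 2: Each treatment cycle will be at least 21 days in length". In Part 1 the first cycle is 28 days and later cycles are 21 days. The main study allows up to five cycles.

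The SAP states no planned or relative dose intensity.

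**The concern.** Dose intensity is meant to show how much drug was delivered per unit of scheduled time. Here the clock stops at the last infusion. Rest periods between cycles are counted, but the one after the final infusion is not. This happens once per subject, so it weighs most on short treatment. At the extreme, a subject who stops after one infusion has a one-day denominator.

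The plan makes such subjects count. Under SAP 1.3.1.1, a dose-limiting toxicity in the Part 1 Core Study ends treatment. SAP 3.9 provides for replacing some early withdrawals, but under SAP 2.1 anyone who received any drug stays in the Safety Set, and SAP 4.5 summarises exposure on that set by treatment group and by the SAP 3.8 subgroups. Groups that differ in early discontinuation can then differ in dose intensity even when dosing up to the stop was identical.

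**Working it through.** The SAP gives no dose-intensity figure to reproduce. The reference value is therefore derived from its schedule.

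**Inputs.** 50 mcg/kg per dose; infusions on Days 1, 3, 5, 8, 10 and 12; 21-day cycles, with 28 days for Part 1 Cycle 1 (SAP 1.3.1.1); the duration formula (SAP 4.5).

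**Intensity implied by the schedule.** 6 × 50 / 21 = 300/21 = 14.3 mcg/kg/day. For Part 1 Cycle 1 it is 300/28 = 10.7.

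**SAP formula, full dose and on schedule.** For k complete cycles the numerator is 300k and the denominator is 21(k − 1) + 12, so the ratio to schedule is 21k/(21k − 9).

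| Stops after | Calculation | mcg/kg/day | Ratio to 14.3 |
|---|---|---|---|
| 1 infusion | 50/1 | 50.0 | 3.50 |
| 4 infusions (Day 8) | 200/8 | 25.0 | 1.75 |
| 1 cycle | 300/12 | 25.0 | 1.75 |
| 2 cycles | 600/33 | 18.2 | 1.27 |
| 3 cycles | 900/54 | 16.7 | 1.17 |
| 5 cycles | 1500/96 | 15.6 | 1.09 |

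Across all 30 possible on-schedule stopping points in five cycles, the lowest value is 1250/85 = 14.7, at Cycle 5 Day 1. In Part 1, one complete 28-day cycle gives 25.0 against 10.7 (2.3 times). Five cycles give 1500/103 = 14.6 against 1500/112 = 13.4 (1.09 times).

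**Masking of under-dosing.** Stopping after four infusions scores the same 25.0 as completing all six, although a third of the cycle's drug was not given. A 33% reduction throughout one cycle gives 201/12 = 16.75, which is 1.17 times schedule.

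**Cases that fall below 14.3**, using departures the SAP permits:

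- 25% reduction throughout: 450/33 = 13.6 after two cycles.
- Infusions on Days 1, 3, 5 and 8 only: 400/29 = 13.8 after two cycles.
- One cycle dosed on Days 1, 3, 15 and 17, using the Days 15–19 make-up window: 200/17 = 11.8.
- Full dose with d days of cumulative delay: 300k/(21(k − 1) + 12 + d) equals 300/21 at d = 9 and is lower beyond that. Five cycles with 14 days of delay give 1500/110 = 13.6.

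**Order by stopping time is not strict.** Stopping at Cycle 2 Day 1 gives 350/22 = 15.9, below the 18.2 for stopping at Cycle 2 Day 12. Stopping at Cycle 3 Day 1 gives 650/43 = 15.1, below the 15.6 for all five cycles.

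**Denominator run to the end of the last cycle started.** Full on-schedule dosing gives 300k/21k = 14.3 for any k. One infusion gives 50/21 = 2.4, and four of six give 200/21 = 9.5.

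**Wording against formula.** In one full cycle drug is given on 6 days, but the formula returns 12. The verbal description and the formula in SAP 4.5 are different quantities.

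**The case against.** The best defence is that little depends on this number. SAP 3.2 calls the study primarily descriptive and plans no formal hypothesis tests. Dose intensity feeds no endpoint, MTD decision or stopping rule. SAP 4.5 also reports total drug, cycles completed, doses taken, missed doses, interruptions and reductions, and lists dosing by subject, so early stopping and under-dosing can be seen elsewhere. The SAP rests on protocol v7.0 and does not cover Parts 3 and 4. All of this stands, and it limits the consequence. It does not make the summary itself informative.

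A reader might infer more than the documents support:

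- *Dose intensity always exceeds plan.* This is true only for full-dose, on-schedule subjects. Permitted reductions, missed or made-up doses, or more than 9 days of delay can bring it below.
- *The earlier the stop, the higher the value.* This holds for a single infusion and across complete cycles, but not day by day.
- *Cohort comparisons are reversed.* No such reversal is shown. The cohorts in SAP 4 run from 5 to 100 mcg/kg/dose, a 20-fold range, and the documents give no discontinuation pattern by cohort.
- *Exposure–safety analyses are distorted.* The SAP plans no analysis of safety against dose intensity, and it leaves PK and pharmacodynamic analysis to a separate document.

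**Conclusion.** The point holds as a definitional flaw in a descriptive summary. Ending the denominator at the last infusion inflates dose intensity by 3.5 times after one infusion, 1.75 times after one cycle and 1.09 times after five, for full-dose, on-schedule subjects on 21-day cycles at 50 mcg/kg. The bias is generally largest for early stoppers. It can give a partly treated subject the same value as a fully treated one, and it makes groups with different early-discontinuation patterns non-comparable on this measure.

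These ratios rest on a reference of 14.3 mcg/kg/day derived here from the schedule, because the SAP defines none. How far the group summaries are affected depends on discontinuation patterns that the documents do not give. The reach is Parts 1 and 2 and the extension.

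**What to change.** Keep last infusion minus first infusion, plus 1, as duration of exposure only, and reword the sentence above the formula to match it. For dose intensity, run the denominator from the first infusion to the planned end of the last cycle started: Day 1 of that cycle plus 20 days, or plus 27 days for Part 1 Cycle 1. Delays between cycles remain counted, because the actual Day 1 of the last cycle is used.

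SAP 4 integrates main and extension data, and SAP Table 3 gives extension cycles as 21 to 28 days. The SAP should therefore also state which cycle length applies there and whether the gap between the two studies counts.

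Add relative dose intensity (received divided by planned), so that cohorts at different dose levels can be read on one scale.

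The cost is a sentence or two in the SAP and one or two derived variables. No new data are needed.

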4.6. Safety Analyses

Study drug exposure analyses will be conducted using the Safety Set.

Safety will be evaluated from adverse events, laboratory results, vital signs, ECG parameters and the changes from baseline in physical examination and medical history.

No formal hypothesis-testing analysis of AE incidence rates will be performed.

All safety analysis will also be performed by subgroup as defined in Section 3.8.

4.6.1. Adverse Events

Adverse events (AEs) will be coded according to MedDRA Version 17.0 using system organ class (SOC) and preferred terms. Adverse events will be graded using the CTCAE v4.03. In the summary tables, subjects may be counted under multiple SOC and PT, but for each SOC and PT

category, subjects are only counted once. If a patient has the same AE on multiple occasions, the worst severity grade (fatal > life threatening > severe > moderate > mild) recorded for the event will be summarized.

Pre-treatment adverse events

All AEs that occurred before the first administration of MT-3724 are considered to be pre-treatment AEs.

Pre-treatment AEs will be summarized using frequency tables for subject count by CTCAE grade and worst CTCAE grade. Separate summary tables will be provided for serious and non-serious events. By-subject listings of pre-treatment AEs will be provided separately for serious and non-serious events. Summary statistics and listings of pre-treatment AEs will be provided for the overall safety population.

Treatment-emergent adverse events

All AEs that have started or worsened after the first administration of MT-3724 up until the last study assessment visit are considered to be treatment-emergent adverse events (TEAEs).

For each TEAE, the investigator will assess the causal relationship to MT-3724 as related and unrelated, where related = possibly, probably or definitely related, and unrelated = unlikely or definitely not related.

TEAEs will be summarized by treatment group using frequency tables for subject count by CTCAE grade and worst CTCAE grade. Separate tables will be provided for non-serious TEAEs, serious TEAEs and all TEAEs (non-serious and serious combined). The following tables will be provided for each of the above categories:

- TEAEs by MedDRA and Worst CTCAE Grade
- TEAEs by MedDRA and Worst CTCAE Grade, Only Grade 3/4/5 Events
- Related TEAEs by MedDRA and Worst CTCAE Grade
- Related TEAEs by MedDRA and Worst CTCAE Grade, Only Grade 3/4/5 Events
- Common TEAEs (occurring in $\geq 10\%$ of subjects) by MedDRA and Worst CTCAE Grade – Only for the overall population and MTD expansion

The following additional tables will be provided for all TEAEs (non-serious and serious combined)

- TEAEs Leading to Permanent Discontinuation by MedDRA and Worst CTCAE Grade
- Related TEAEs Leading to Permanent Discontinuation by MedDRA and Worst CTCAE Grade
- TEAEs Leading to Dose Reduction by MedDRA and Worst CTCAE Grade
- Related TEAEs Leading to Dose Reduction by MedDRA and Worst CTCAE Grade
- TEAEs Leading to Dose Interruption / Delay by MedDRA and Worst CTCAE Grade

- Related TEAEs Leading to Dose Interruption / Delay by medDRA and Worst CTCAE Grade

The following by-subject listings of TEAEs with the corresponding MedDRA PT, worst CTCAE grade, relatedness outcome and seriousness (where applicable) will be provided:

- Non-serious TEAEs Grade 3/4/5
- Serious TEAEs (all CTCAE grades)
- TEAEs Leading to Dose Interruption / Delay
- TEAEs Leading to Dose Reduction
- TEAEs Leading to Permanent Discontinuation
- TEAEs Declared as Dose Limiting Toxicities
- TEAEs Leading to Death

4.6.2. Laboratory Data

Clinical laboratory values will be expressed in SI units.

Quantitative laboratory data will be summarized by treatment group, parameter and scheduled time points using descriptive statistics. The summary tables will be presented for the original data as well as for the difference from baseline. In the event of repeat values, the average value per study day/time will be used. Local hematology lab results will be primarily considered for summary tables; if no local lab results are available, central lab results will be used. Non-negative results will be listed for qualitative variables. Microglobulin, immunology, and complement samples, as well as Serum cytokine results from the central lab will be included in the summary tables.

Shift tables will be produced that summarize the maximum shifts from baseline to worst value for hematology, chemistry, and coagulation lab categories using CTCAE toxicity grades for relevant laboratory parameters. Scatter plots or box and whisker plots of selected lab tests over time may be presented where appropriate. Unscheduled visits may contribute to worst visits, as applicable. Both local and central hematology lab results will be considered for worst values.

All laboratory data will be provided in data listings, where laboratory values outside the normal range will be flagged with “H” (high) or “L” (low), as well as the CTCAE grade, if applicable.

Unscheduled visits will not be summarized in tabulations. They will only be included in data listings and/or shift tables, as appropriate.

4.6.3. Vital Signs

Vital signs parameters include systolic and diastolic blood pressure, heart rate, respiration rate, body temperature and body weight.

The actual value and change from baseline within each on-study evaluation will be summarized by treatment group. The pre-dose measurement will act as baseline for a given visit; post-dose measurements will be compared to pre-dose measurements within each visit.

Vital sign measurements will be presented for each subject in a data listing by treatment group.

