¹ Height and weight are collected at the Screen visit. Weight is collected again at final safety visit 14-28 days after last infusion. The MT-3724 dose is calculated using Screening visit weight.

² For the first two infusions in Cycle 1 (Doses 1 & 2), vital signs (temperature, blood pressure, pulse, and respiration rate) will be collected at pre-dose prior to initiation of dosing on each dosing day, at 20, 40 and 60 min (\pm 5 min), at 90 min (\pm 10 min), at 2 hours (\pm 15 min) and no less than hourly (\pm 15 min) until the infusion is completed. For all other infusions, vital signs should be collected prior to the initiation of the infusion and at the conclusion of the infusion (\pm 15 min). Beyond these times and at all other infusions, subjects should be monitored as clinically indicated. The frequency of interim monitoring during and following all infusions beyond the second infusion should be determined by the Investigator based on the subject's clinical condition. In addition, in all subjects, orthostatic vital signs will be performed as needed after all doses prior to the subject standing or ambulating for any reason during the observation period.

³ Calculate estimated creatinine clearance by Cockcroft Gault formula.

⁴ All female subjects of child bearing potential must have a urine pregnancy test performed prior to the first dose of each new cycle of MT-3724 beginning with the first cycle and continuing through the last cycle. Pregnancy test should be done within 72 hours prior to the first dose of each new cycle.

⁵ Lymphocyte subset samples must be processed and shipped to the Central Laboratory according to Site Reference Manual and Laboratory Manual instructions. The baseline flow cytometry sample should be drawn at the Screening Visit whenever possible. If not obtained at the Screening Visit, the baseline flow cytometry sample may be drawn on Dose Day 1 prior to initiation of dosing. The sample drawn on Cycle 1 Day 8 (Visit 5, Dose 4) during the first cycle of MT-3724 should be drawn PRIOR to the initiation of Dose 4 infusion. Additionally, **Part 1 only: FOR SUBJECTS WITH CLL, flow assessment for minimal residual disease (MRD) will be obtained at Baseline and the Final Safety Assessment** respectively.

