		Visit 2 Day 1 Dose 1	Visit 3 Day 3 Dose 2	Visit 4 Day 5 Dose 3	Visit 5 Day 8 Dose 4	Visit 6 Day 10 Dose 5	Visit 7 Day 12 Dose 6	Day 16-25			
12-Lead ECG ¹⁰	X (only when clinically indicated)										
Cancer Histology	X (Confirm history) X (repeat only when clinically indicated)										

Abbreviations: ADA: anti-drug antibodies; ALT: alanine aminotransferase; AST: aspartate aminotransferase; BUN: blood urea nitrogen; Ca: calcium; CBC: complete blood count; Cl: chloride; CO₂: carbon dioxide; CPK: creatine phosphokinase; Cr: creatinine; CT: computed tomography; ECG: electrocardiogram; ECOG: Eastern Cooperative Oncology Group; GGT: gamma-glutamyl transferase; HepBAb: hepatitis B antibody; HepBAg: hepatitis B surface antigen; HepCAb: hepatitis C antibody; HIV: human immunodeficiency virus; IFN- γ : interferon gamma; IL-6: interleukin 6; K: potassium; LDH: lactate dehydrogenase; Mg: magnesium; MRD: minimal residual disease; NA: sodium; PET: positron emission tomography; PK: pharmacokinetic; TNF α tumor necrosis factor alpha

¹ Height and weight are collected at the Screening Visit. Weight is collected again at Final Safety Visit 14-28 days after last infusion. MT-3724 dose is re-calculated using Screening Visit weight if subject's weight has changed by $\pm 10\%$ from MT-3724_NHL_001_US study, the dose OR subject's mcg/kg/dose must be changed due to MTD identification.

² See Protocol Appendix 3. CT scans will be performed for tumor assessment at screening and Final Safety Visit. Additional tumor assessment (s) will be performed per investigator. Where clinically indicated, PET scan may also be performed per Investigator discretion.

³ For all infusions, all cycles, vital signs (temperature, blood pressure, pulse, and respiration rate) should be collected prior to the initiation of the infusion and at the conclusion of the infusion. Beyond these times subjects should be monitored as clinically indicated. The frequency of interim monitoring during and following all infusions should be determined by the Investigator based on the subject's clinical condition. In addition, in all subjects, orthostatic vital signs will be performed as needed after all doses prior to the subject standing or ambulating for any reason during the observation period

⁴ Calculate estimated creatinine clearance by Cockcroft Gault formula.

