3.4. Baseline Definitions

For both the Main and Extension studies, unless noted otherwise, baseline will be defined as the most recent measurement prior to the first administration of MT-3724 in the Main Study.

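### SAP 4.6.3 resets the vital-sign baseline at every dosing visit, so the change tables for Parts 1 and 2 and the extension leave out blood-pressure shifts that build up between doses

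*SAP*

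**What the plan says.** SAP 3.4 sets a general rule for the main and extension studies, subject to any exception stated elsewhere: "baseline will be defined as the most recent measurement prior to the first administration of MT-3724 in the Main Study".

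SAP 4.6.3 makes such an exception. It first defines the scope: "Vital signs parameters include systolic and diastolic blood pressure, heart rate, respiration rate, body temperature and body weight". It then states what is tabulated: "The actual value and change from baseline within each on-study evaluation will be summarized by treatment group". The next sentence fixes the baseline for that change: "The pre-dose measurement will act as baseline for a given visit; post-dose measurements will be compared to pre-dose measurements within each visit". The section ends with "Vital sign measurements will be presented for each subject in a data listing by treatment group".

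Weight follows a different schedule from the other vital signs. Footnote 1 to the main-study schedules in SAP 1.3.4 says "Height and weight are collected at the Screen visit. Weight is collected again at final safety visit 14-28 days after last infusion". The extension footnote says the same: "Height and weight are collected at the Screening Visit. Weight is collected again at Final Safety Visit 14-28 days after last infusion". The dosing-day vital signs in footnote 2 (main study) and footnote 3 (extension) are temperature, blood pressure, pulse and respiration, without weight.

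**The concern.** A within-visit comparison answers one question: what happens during and just after an infusion. In Part 2 the infusion lasts about 2 hours. After the first two infusions of Cycle 1, the only required readings are one before and one at the end of the infusion. A change column built on that pair says nothing about where the subject stands relative to the untreated state.

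The slower question matters for this drug. Protocol 2.2.1 lists capillary leak syndrome among the important identified risks. It reports two cases in this study at 75 µg/kg/dose, a dose level this SAP analyses. Protocol 2.2.2 bases suspicion on at least two of hypoalbuminemia, hypotension, and edema and/or weight gain within the same cycle, which is a horizon of days. The version 11 rationale in Protocol 12.1 places the events within a few days of initial dosing or of re-dosing. What is at stake is the tabulated within-subject comparison of on-treatment blood pressure with its pre-treatment value.

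**Working it through.** **1. Where the two baselines differ.** The reading before the first dose on Cycle 1 Day 1 serves as baseline under both rules, so they agree at that visit. They part from the second dose onward. With the planned maximum of 5 cycles of 6 doses there are 5 × 6 = 30 dosing visits in the main study. At 30 - 1 = 29 of them the 4.6.3 baseline is an on-treatment value.

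**2. Comparison with the rest of the SAP.**

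| Data | SAP section | Baseline |
|---|---|---|
| Laboratory | 4.6.2 | Difference from baseline; no per-visit reset |
| Vital signs | 4.6.3 | Each visit's own pre-dose reading |
| Physical examination | 4.6.4 | Shift from baseline to each later assessment |
| ECG | 4.6.5 | Screening recording, for all on-treatment values |
| ECOG | 4.6.7 | Shift from baseline to each later assessment |

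Only vital signs are reset. Protocol v11.0, sections 9.3.3 and 9.3.3.3, uses the last valid value before study drug for Parts 3 and 4.

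**3. Illustration (assumed drift; no such figure is in the documents).** Let the pre-dose systolic pressure at dosing visit k of Cycle 1 be B_k = B_1 - d(k - 1), for k = 1 to 6, with no change within a visit.

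- Change under 4.6.3: B_k - B_k = 0 at every visit.
- Change under 3.4: B_k - B_1 = -d(k - 1), so at the sixth dose (Day 12) it is -5d.

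| Assumed d (mmHg per dosing visit) | Day 12 change, 4.6.3 | Day 12 change, 3.4 |
|---|---|---|
| 2 | 0 | -10 |
| 5 | 0 | -25 |
| 8 | 0 | -40 |

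The zero follows from the assumption of flat readings within visits. Any within-visit movement would appear in the 4.6.3 column, but the between-visit part still would not.

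**4. Evaluations the 4.6.3 rule does not reach.** SAP Table 1 schedules vital signs at Visit 8 (Day 16-19), Visit 9 (Day 23-25, Part 1 only) and the final safety assessment. No dose is given there, so there is no pre-dose reading. Weight has no pre-dose and post-dose pair at any visit. The SAP does not say which baseline applies in these cases. The 3.4 default is the natural reading.

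**5. Gap between weight readings in the main study.** The last dose of five full cycles at minimum length falls on Day 28 + 3 × 21 + 12 = 103 in Part 1 and Day 4 × 21 + 12 = 96 in Part 2. Adding 14 to 28 days puts the second weight on Days 117-131 or 110-124. After a single cycle (last dose Day 12), the same rule gives Days 26-40. No weight is scheduled in between.

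**The case against.** The strongest reply is that little is lost. Within-visit change is a sensible measure for an infused drug, and the study is descriptive with no planned tests (SAP 3.2). SAP 4.6.3 also summarizes actual values at each evaluation and lists every reading. If the same subjects attend each visit, the difference between two visit means equals the mean within-subject change, so the 25 mmHg fall in the middle row of the illustration would be plain from the means. Planned Part 1 cohorts are 3 to 6 subjects, small enough to read from the listings. Hypotension, edema or capillary leak reported as adverse events are tabulated by worst grade (4.6.1). Laboratory and physical-examination shifts are tabulated too.

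Most of this stands, and it limits the point. What remains is that by-visit means do not show the spread of individual changes. They also stop being comparable once subjects miss doses or withdraw, because successive means then describe different people.

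Three stronger readings are tempting and are not supported:

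- **That a sustained fall in pressure or a weight gain cannot appear as a change at all.** If 3.4 governs visits without a dose and weight, a shift still present at Visit 8, Visit 9 or the final visit would be tabulated. The SAP is silent, not contrary.
- **That the baseline rule is why a passing weight gain is missed.** That is a limit of the collection schedule, and no choice of baseline adds a reading.
- **That Parts 3 and 4 are affected.** This SAP is based on protocol v7.0. Protocol v11.0 uses the pre-drug baseline and schedules weight on dosing days (Table 1-1).

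**Conclusion.** The point holds in a limited form. On dosing days in Parts 1 and 2 and the extension, SAP 4.6.3 tabulates only within-visit change, departs from SAP 3.4, and is the only safety domain in the SAP to reset its baseline by visit. A between-dose blood-pressure shift is absent from the change summaries but present in the actual values and listings. The size cannot be taken from the documents. The range of -10 to -40 mmHg against 0 rests wholly on the assumed drift of 2 to 8 mmHg per dosing visit and on flat readings within visits. The baseline for weight and for visits without a dose is unstated and should be settled in the same edit. No planned conclusion is shown to change. The case for acting is that the amendment restores a within-subject safety comparison at very small cost.

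**What to change.** In SAP 4.6.3:

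- Tabulate change from the Section 3.4 baseline (last value before the first MT-3724 dose) at every pre-dose, post-dose and non-dosing evaluation.
- Keep the within-visit change as an additional table, labelled as describing infusion effects.
- State that the 3.4 baseline also applies to visits without a dose and to weight, so that weight change runs from screening to the final visit. Note that changes between those two readings are not captured.

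The cost is one extra set of tables and a few sentences of SAP text. All the readings needed are already collected.
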